#### 8.2. Risk-to-Benefit Rationale

The registry will not require the use of any procedure and / or test and / or device different from those required by routine clinical practice, enrolled patients will not be exposed to additional risks when compared to routine clinical practice.

The only additional known risk is the possible loss of confidentiality. Controls have been put in place to prevent loss of confidentiality.

### 9. Adverse Events and Safety Monitoring

Clinical AEs are defined as any untoward medical occurrence in a patient, whether device-related or not. Pre-existing conditions will not be considered AEs unless there is worsening of the condition after enrollment. All AEs will be documented in the patient's permanent medical record, recorded on the appropriate eCRF, and reported in accordance with applicable national regulations. Emergency contact information for AE reporting can be found on the site's ICF.

9.1. Anticipated Adverse Events

Anticipated adverse events are medical complications that are known to be associated with patients undergoing endovascular stent grafting of peripheral vessels. See Section 8, Risk Assessment.

### 9.1.1. Adverse Event Relationship

Each reported AE will be assessed by the investigator for its primary suspected relationship to the device, procedure, or disease, as further described below:

- VBX Stent Graft-related
  - The functioning or characteristics of the device caused or contributed to the AE.
- Registry Procedure-related
  - The procedure (and not the device) caused or significantly contributed to the AE.
- Gore Accessory Use-related
  - Any additional Gore devices that were used during the index procedure and / or reintervention caused or contributed to the AE.
- Unrelated to VBX Stent Graft or procedure
  - An AE which cannot be attributed to the device, procedure, access.

Only one primary relationship will be assigned to each reported AE.

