### 3.2.3. Secondary Endpoint(s)

Selected events that are illustrative of the device's potential impact to a patient from a safety perspective, overall device function described as patency or device durability captured as device integrity are the registry's secondary endpoints. Possible endpoint events will be identified from site reports with some secondary endpoints within scope of CEC adjudication.

The secondary endpoints for the VBX 17-04 registry are the following:

- VBX Stent Graft-related death within 30 days post-treatment
- Procedural-related death within 30 days post-treatment
- Procedural-related SAE within 30 days post-treatment
- VBX Stent Graft patency (primary, primary assisted, secondary) through 30 days post-treatment
- VBX Stent Graft patency (primary, primary assisted, secondary) through five years post-treatment
- VBX Stent Graft-related SAE through five years post-treatment
- VBX Stent Graft-related death through five years post-treatment
- Loss of device integrity through five years post-treatment
- Limb salvage through five years post treatment

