6.2.3. Device Accountability and Storage

Information on Gore accessory devices used during the procedure may be collected. This may include additional non-VBX Stent Graft devices, balloon catheters, and sheaths.

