9.4. Clinical Events Committee

An independent Clinical Events Committee (CEC) will review safety-related, clinical events during the registry to ensure the consistency of endpoints reported by the site. The VBX 17-04 CEC will be comprised of an interdisciplinary team of three members with pertinent expertise who are not directly involved in the conduct of the registry.

The scope of the CEC activity includes the following:

General review and adjudication of SAE's to include:

- a. Adjudication on the serious adverse event (SAE) designation
- b. Adjudication on the relationship of the SAE to the study device, procedure, or unrelated

This committee will operate under pre-specified procedures as outlined in the CEC Charter. The frequency of data review and other roles and responsibilities of the CEC will be specified in the CEC Charter.

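### Accessory-related events feed no endpoint and events of undetermined cause have no class of their own, so procedure- and VBX-related SAE and death rates can be understated

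*Protocol*

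**What the plan says.** Protocol 9.1.1 has the investigator choose the primary suspected relationship of each AE from four classes:

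- VBX-related, for the study device itself, where any contribution is enough: "The functioning or characteristics of the device caused or contributed to the AE".
- Procedure-related, for the implant procedure, with a higher threshold: "The procedure (and not the device) caused or significantly contributed to the AE".
- Accessory-related, for the sponsor's other products, again with any contribution enough: "Any additional Gore devices that were used during the index procedure and / or reintervention caused or contributed to the AE".
- Unrelated, the residual class: "An AE which cannot be attributed to the device, procedure, access".

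The classes are exclusive: "Only one primary relationship will be assigned to each reported AE". Protocol 6.2.3 indicates which accessories may be recorded: "This may include additional non-VBX Stent Graft devices, balloon catheters, and sheaths".

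The endpoints that depend on relationship (Protocol 3.2.2 and 3.2.3, SAP 2.1.1 and 2.1.2) use two of these classes only. VBX-related SAE and death are counted at 30 days and at five years. Procedure-related death and SAE are counted at 30 days, the latter as "Procedural-related SAE within 30 days post-treatment".

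The CEC has a shorter list. Protocol 9.4 gives its task as "Adjudication on the relationship of the SAE to the study device, procedure, or unrelated", and SAP 5.0 repeats the three classes. Protocol 3.2.3 puts only some secondary endpoints within CEC scope and does not name them.

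**The concern.** The registry tests no hypothesis and has no comparator. Its product is a set of percentages with confidence intervals, so a rule that sorts events wrongly goes straight into the reported result.

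Two rules deserve attention. First, sheaths and balloons are tools of the procedure. A separate class for the sponsor's own tools, with no endpoint attached, can make the 30-day procedural SAE and death rates depend on who made the accessory. Second, a residual class defined by inability to attribute, with no undetermined option beside it, invites events of unknown cause to be recorded as unrelated. Those patients are then counted as free of the event, just where information is poorest.

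**Working it through.** **1. The plan's own figure.** The SAP gives a margin of error below 6% with n = 280. The normal half-width is 1.96 × √(p(1−p)/280):

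- p = 0.971 (assumed clinical success): 1.97 points.
- p = 0.936 (assumed freedom from device- or procedure-related SAE): 2.87 points.
- p = 0.5: 5.86 points.

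With exact intervals, which SAP 6.0 specifies, 272/280 gives 94.4% to 98.8% (half-width 2.16), 262/280 gives 90.0% to 96.1% (half-width 3.06), and 140/280 gives a half-width of 6.01. The stated margin reproduces at the planning rates and is not in dispute. It describes sampling error only and does not cover misclassification.

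**2. Each class traced to an endpoint.**

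- VBX-related: primary endpoint, 30-day death, five-year SAE and death; CEC class device.
- Procedure-related: 30-day SAE and death; CEC class procedure.
- Accessory-related: no endpoint; no CEC class.
- Unrelated: scored as no event; CEC class unrelated.
- Undetermined: absent from both lists.

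**3. Three cases.**

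*Access-vessel injury from a sheath at the index procedure.* With another maker's sheath, procedure is the class that fits, and the event counts. With a Gore sheath, accessory also fits. The thresholds differ: accessory needs a contribution, procedure a significant one. An event to which both contributed modestly meets only the accessory definition. On investigator coding it then leaves the procedural endpoints. If the CEC reviews it, it must be re-sorted, and no rule says where.

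*VBX device and accessory both contributed.* Both definitions are met and only one may be chosen. If accessory is chosen, the VBX-related count loses an event. This is the only route by which the accessory class touches the VBX endpoints.

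*Death at day 20, cause not established.* It cannot be attributed to device, procedure or access, so read literally it is unrelated. Protocol 10.3.4 and 10.3.5 and SAP 6.0 (iv, v) drop missing outcomes, but a recorded unrelated code is not missing. The patient stays in the denominator without an event. Protocol 9.1.5 treats death as the outcome of an AE, so the code carries into the death endpoints. Protocol 5.8 accepts telephone follow-up in some cases, so thin information is foreseeable.

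**4. Size.** One patient moved changes a rate by 1/280 = 0.36 points. In a treatment category filled to its cap (Protocol 4.1.1), the change is 1/140 = 0.71, 1/90 = 1.11 or 1/50 = 2.00 points. Smaller denominators at later years raise it further.

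For scale only: freedom of 93.6% is 262 of 280, so 18 patients have an event (18/280 = 6.43%). The documents give no share for accessory or undetermined events. For assumed shares of 10%, 20% and 30% of the 18:

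- 10%, 2 patients: 16/280 = 5.71%.
- 20%, 4 patients: 14/280 = 5.00%.
- 30%, 5 patients: 13/280 = 4.64%.

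Even the last, 95.4% freedom, lies inside the exact interval of 90.0% to 96.1%. The 6.4% pools device- and procedure-related SAEs, and the registry reports no such pooled endpoint. These lines show scale and are not an estimate.

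**The case against.** The strongest reply is that the CEC adjudicates the seriousness and relationship of SAEs. Its list has no accessory class, so an accessory-coded SAE must be placed again and may well return to procedure. An access injury also sits badly in the unrelated class, whose definition names access. A mapping rule could be in the CEC Charter, which is not among the documents, or in SAP section 9.0, which has no content in the available text. This stands as far as it goes, and it means that bias cannot be asserted as fact. It does not close the gap: no visible rule fixes the mapping, only some unnamed secondary endpoints are in CEC scope, and neither document says whose assessment governs each one. An endpoint derivation belongs in the SAP.

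It is also fair to say that an investigator is not obliged to code accessory whenever a Gore product was in use, since the question is the primary suspected cause. That leaves coding to vary between sites. An event caused only by another Gore device is rightly not VBX-related, and leaving it out does not bias the primary endpoint.

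On undetermined events, no text says that unexplained deaths default to unrelated. A suspected contribution is enough for VBX-related, and Protocol 9.1.5 requires an effort to obtain source documents or a death certificate. The literal reading is therefore one reading, though no rule excludes it.

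Finally, a separate accessory class is reasonable where the VBX device is one component of a branched or chimney repair, and relationship is recorded for every AE, so the events are not lost. That supports keeping the label. It does not support leaving the label outside every endpoint.

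**Conclusion.** The point holds as a possible downward bias of unknown size. The class definitions can make the 30-day procedure-related SAE and death rates depend on the accessory's manufacturer. They can also score SAEs and deaths of undetermined cause as non-events in the 30-day and five-year VBX-related endpoints and the 30-day procedure-related endpoints. The first effect needs investigator coding to stand, or the CEC to choose unrelated. The second needs the literal reading of the unrelated class.

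A reader might infer that the rates are in fact understated, that accessory coding generally biases the VBX-related endpoints, or that every unexplained death will be counted as non-device. The documents support none of these. CEC review may restore accessory events to procedure, the VBX endpoints are exposed to accessory coding only when both causes contributed, and no rule sends unexplained events to unrelated. Nor can a percentage reduction be read from the pooled 6.4%. The only figure that needs no assumed share is 0.36 points per patient moved, on 280 evaluable patients.

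**What to change.** Amend Protocol 9.1.1 and 9.4 and SAP 2.1, 5.0 and 6.0 together:

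1. Count accessory-related SAEs and deaths arising from the index procedure as procedure-related. Keep accessory as a sub-class, show accessory events at reintervention separately, and give the CEC the same list as the investigator.
2. Define unrelated as a cause other than device, procedure or accessory having been identified. Add a class for relationship undetermined. Report device- and procedure-related SAE and death rates without and with undetermined events, as lower and upper bounds.
3. State that the CEC relationship governs all SAE and death endpoints.

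The cost is one extra eCRF and CEC option, one derivation rule and one extra table column, with slightly higher reported event rates. Protocol 9.1.3 already collects relationship for each AE, so the accessory mapping can be applied to recorded data, given a check of whether each event arose at the index procedure or at a reintervention. For the undetermined class, the CEC would have to look again at SAEs and deaths already coded unrelated. No treatment or visit changes.

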9.1.2. Adverse Event Classification

Each AE will be assessed by the investigator to determine if it is serious or nonserious, according to ISO 14155:2011. An SAE is defined as satisfying any of the following:

#### Serious Adverse Event

A serious adverse event is an adverse event that

- Led to death
- Led to serious deterioration in the health of the patient that either resulted in:
  - A life-threatening illness or injury, or
  - A permanent impairment of a body structure or a body function, or
  - o In-patient or prolonged hospitalization, or
  - Medical or surgical intervention to prevent life-threatening illness or injury or permanent impairment to a body structure or a body function
- Led to fetal distress, fetal death, or congenital abnormality or birth defect.

**NOTE:** Emergency room visits and 23-hour observations may not constitute hospitalization.

Non-Serious Adverse Events: Any AE not meeting the above definition of serious.

## 9.1.3. Adverse Event Reporting and Coding

AEs will be reported on the appropriate eCRF and documented in the patient's permanent medical record. AE reporting will start from enrollment (when informed consent is obtained). The investigator at each site is ultimately responsible for reporting AEs to the sponsor.

The following information on each reported AE will be collected:

- Adverse event name
- Adverse event onset date
- Relationship
- Classification (serious or non-serious)
- Treatment
- Outcome
- Resolution date

AEs will be coded using the Medical Dictionary for Regulatory Activities (MedDRA).

- 9.1.4. Adverse event submission guidelines:
  - AE reporting begins once the patient is enrolled in the registry. All AEs should be reported from enrollment through registry completion / discontinuation.
  - Provide a diagnosis if possible. If unable to provide a diagnosis, report the symptoms as separate events. AEs should be reported using the full name without abbreviations or narratives.
  - AEs with an outcome status of "ongoing" should be assessed at each follow-up evaluation to determine if the event has resolved. AEs ongoing at study completion / discontinuation should be left as "ongoing" on the AE case report form.

The site principal investigator or designee must report SAEs to the registry sponsor as soon as possible after onset, observation, or first reporting of the occurrence, and in accordance with applicable national regulations. It is the responsibility of each investigator to report all SAEs to the reviewing EC, according to national regulations and EC requirements. A copy of the EC report will be forwarded to the sponsor. Source documents must be submitted upon request (*e.g.*, histopathology findings, catheter lab reports, etc.). All source documents must be blinded using only the patient's unique study identifier and forwarded to the sponsor.

9.1.5. Patient Death

In this clinical investigation, death is not considered an AE, but rather the outcome of an AE. Any ongoing / unresolved AEs will be considered as ongoing at the time of death or registry withdrawal. An effort must be made to collect source documentation or death certificate in the case of death.

### 9.2. Unanticipated Serious Adverse Device Effects (USADE)

An Unanticipated Serious Adverse Device Effect (USADE) is defined in ISO 14155 as any serious adverse effect on health or safety or any life-threatening problem or death caused by, or associated with, a device, if that effect, problem, or death was not previously identified in nature, severity, or degree of incidence in the current version of the protocol, IB or IFU. If a complication occurs that the investigator believes may be a potential USADE, the site

should immediately contact the sponsor to determine reporting requirements. In addition, when there is a reason to believe a device may have malfunctioned, causing potential harm to a patient, the site should immediately notify the sponsor.

All USADEs must be documented by the investigator including the date of onset, a complete description of the event, possible reason(s) for the event, severity, duration, actions taken, and outcome.

### 9.3. Device Deficiency

A device deficiency is defined as an inadequacy of a medical device with respect to its identity, quality, durability, reliability, safety, or performance of the study device. Device deficiencies include damages, malfunctions, use errors, or inadequate labeling whether such a condition is experienced in the stage of design, supply, storage, or use. Device deficiency may not be associated with an AE suffered by a registry patient but will need to be reported to Gore immediately upon identification by the site.

The following information on each reported deficiency will be collected:

- Description of deficiency
- Date of occurrence
- Batch code and lot number of the affected device
- Related patient AE information (if applicable)

Device deficiency information on Gore accessory devices used during the procedure may be collected. This may include additional non-VBX Stent Graft devices, balloon catheters, and sheaths.

9.4. Clinical Events Committee

An independent Clinical Events Committee (CEC) will review safety-related, clinical events during the registry to ensure the consistency of endpoints reported by the site. The VBX 17-04 CEC will be comprised of an interdisciplinary team of three members with pertinent expertise who are not directly involved in the conduct of the registry.

The scope of the CEC activity includes the following:

General review and adjudication of SAE's to include:

- a. Adjudication on the serious adverse event (SAE) designation
- b. Adjudication on the relationship of the SAE to the study device, procedure, or unrelated

This committee will operate under pre-specified procedures as outlined in the CEC Charter. The frequency of data review and other roles and responsibilities of the CEC will be specified in the CEC Charter.

### 10. Statistical Analysis

10.1. Statistical Approach

10.2. Sample Size Determination

Two hundred eighty (280) patients will be implanted with the VBX Stent Graft across multiple pathologies. The sample size of 280 patients was considered adequate to estimate study outcomes with reasonable precision and to have sufficient patients enrolled within each indication. The sample size was determined by Gore to characterize broad device use across device indications. In combination with strategic selection of participating registry sites, this number should be sufficient to describe the study endpoints with less than 6% margin of error.

10.3. Data Analysis

10.3.1. Timing of Analyses

There are no planned interim analyses or guidelines for early termination / registry stoppage due to the commercial nature of the VBX Stent Graft.

10.3.2. Analysis Populations

All enrolled patients meeting the inclusion / exclusion criteria and treated with the VBX Stent Graft will be included in the primary and secondary endpoint analyses.

10.3.3. Pooling of Data

It is expected that the VBX Stent Graft may be used in treatments that may differ by type of treatment (elective vs. emergent), patient risk (high vs. low / moderate) or role in treatment (primary repair vs. combinatorial repair). In each of these indications, the mechanism of introduction and device delivery will remain the same along with intended device function (lesion exclusion / vessel patency). The use of balloon-expandable stent grafts a well-known and practiced endovascular therapy that is not expected to differ between selected registry sites. As such, there is no concern in regards to pooling data from different European countries or sites together for analysis.

Gore may perform analyses to detect differences in device experience according to gender, age, or pathology treated.

10.3.4. Statistical Analysis of Primary Endpoint(s)

Tables of the primary endpoints procedural success and freedom from VBX Stent Graft-related SAEs at 30 days will be reported. Data will be presented descriptively with confidence intervals.

Missing data at the time of analysis will not be included in the denominator.

10.3.5. Statistical Analysis of Secondary Endpoint(s)

Tables of the secondary endpoints—device related death at 30 days, procedural related death at 30 days, procedural related SAE at 30 days, device patency at 30 days and on yearly basis, device-related SAEs, device-related death, loss of device integrity and limb salvage at yearly basis will be reported. Data will be presented descriptively with confidence intervals, where appropriate.

Missing data at the time of analysis will not be included in the denominator.

10.3.6. Analysis by Treatment Category

Individual device treatment indications will be categorized into larger groups "Treatment Categories" based upon either similar device function or purpose. Combining treatment indications into larger groups will permit the analysis of general treatment concepts where an analysis based upon on an individual indication would not be feasible.

10.3.7. Analysis of Individual Treatment Indications

At the conclusion of enrollment, an evaluation of the distribution of device use across individual pathologies will be performed. If feasible, device experience by indication will be tabulated for descriptive analysis.

### 11. Ethical and Regulatory Considerations

11.1. Statement of Compliance

The requirements of Clinical Investigation of Medical Devices for Human Patients Good Clinical Practice (ISO14155:2011), International Conference on Harmonization Good Clinical Practice (ICH E6 (R2)), and Food & Drug Administration (FDA) applicable regulations have been incorporated into applicable Clinical Quality System procedures.

The following are applicable to this registry:

ICH-GCP E6	International Conference on Harmonization Regulations Guideline For Good Clinical Practice
Medical Device Directive (93/42/EEC) Article 15 Annex X	Council Directive 93 / 42 / EEC of 14 June 1992
Amendment to the MDD (2007/47/EC) Article 15 Annex X	Directive 2007 / 47 / EC of the European Parliament and of the Council of 5 September 2007
ISO 14155:2011 (E)	Clinical investigation of medical devices for human patients – Good clinical practice

#### 11.2. Compliance Responsibilities

Gore will conduct the registry in accordance with all applicable regulations and laws. Gore will be responsible for documenting that investigators have the necessary skills, training, and information to properly participate in the registry. Gore will confirm proper monitoring of the registry and verify that the site has obtained Ethics Committee (EC) approval prior to enrollment. Gore will provide information to the investigators and the reviewing ECs concerning the progress of and any new material information about the registry.

The investigator will conduct the registry in accordance with all applicable regulations and laws, any relevant agreements, the registry protocol, and all approval conditions of the reviewing EC. Any additional requirements imposed by the EC shall be followed. The investigator will verify EC approval is obtained prior to enrollment, maintained throughout the course of the registry, and that all EC reporting requirements are met. The investigator is responsible for protecting the rights, safety, and welfare of patients under their care. The investigator is also responsible for ensuring that informed consent is properly obtained.

The registry shall be conducted in accordance with the ethical principles that have their origin in the Declaration of Helsinki.

